### **4.3 Inclusion of Women and Minorities**

Women and minorities will be included.

## **REGISTRATION PROCEDURES**

### **5.1 Patient Registration**

To register a patient, the following documents must be completed by the sub-site research team or UC research team and securely e-mailed to the UC Study Project Manager and UC PI:

- Copy of all baseline tests required per the protocol calendar. Tests must be within the protocol specified windows and assessed for clinical significance.
- Signed consent.
- Consent documentation note.
- Source documents sufficient to support verification of every inclusion & exclusion criteria.

Upon UC PI confirmation of eligibility, to complete the registration process, the Project Manager will:

- Assign a patient study number (see 7.3.4 Assignment of Screening/Study Number)
- Register the patient on the study.
- Assign the patient into one of the two arms after using R software
- E-mail the patient study number and arm to the participating site and ensure site is notified of patient's eligibility status.

### **5.2 General Guidelines**

Following registration, patients should begin protocol treatment within 28 days. Issues that would cause treatment delays should be discussed with the Principal Investigator. If a patient does not receive protocol therapy following registration, the patient's registration on the study may be canceled. The Study Project Manager should be notified of cancellations as soon as possible.

## **BIOMARKER, CORRELATIVE, AND SPECIAL STUDIES**

## 6.1 Biomarker Plan

### List of Biomarker Assays in Order of Priority

Priority	Biomarker Name	Biomarker Assay	Biomarker Type and Purpose	M/O	Timing	Specimen	Quantity Needed	Laboratory
1	Peripheral Blood Immune Phenotypes	Flow Cytometry	Exploratory  To determine the change in peripheral blood immune populations in response to metformin, pembrolizumab or combination.	M	Pre-treatment Post-lead-in During combination	Peripheral blood in EDTA tubes	20 mls	CTO/[name]/ [name]
2	NK cell infiltration and anti-tumor activity	Immunofluorescence	Integrated  To determine NK cell infiltration after treatment with metformin and pembrolizumab .	O	Pre-treatment During combination	FFPE slides	5 slides each or block	[name]
3	NK Effector Functions	NK Cytotoxicity Assays	Exploratory  To determine NK cell activation and cytotoxic activity after treatment with metformin and pembrolizumab .	O	Pre-treatment Post-lead-in During combination	NK cells isolated from EDTA tubes	40 mls	[name]
4	NK Effector Functions	Isolight Analysis	Exploratory  To determine NK cell polyactivation after treatment with metformin and pembrolizumab .	O	Pre-treatment Post-lead-in During combination	PBMCs/ NK cells isolated from EDTA tubes	20 mls (can be combined with #3)	CTO

Priority	Biomarker Name	Biomarker Assay	Biomarker Type and Purpose	M/O	Timing	Specimen	Quantity Needed	Laboratory
5	Cytokine Levels	ELISA	Exploratory  To determine the cytokine response before and after metformin, pembrolizumab and combination	O	Pre-treatment Post-lead-in During combination	Plasma isolated from EDTA tubes and 5mls from red top serum tube	10 mls (5 mls can be collected from samples for which PBMCs are isolated)	CTO/[name]
6	STAT-3 Expression	Nanostring Technology	Exploratory  To determine if metformin and pembrolizumab result in decreased STAT-3 in tumor and immune cells.	O	Pre-treatment During combination	FFPE scrolls and 5 slide	1 scroll each, 5 FFPE slides	[name]
7	NKG2D soluble ligands	ELISA	Exploratory  To determine if metformin and pembrolizumab result in release of NKG2D soluble ligands.	O	Pre-treatment Post-lead-in During combination	Plasma isolated from EDTA tubes	5 mls (can be collected from samples for which PBMCs are isolated)	[name]
8	Tissue Biomarkers	IHC	Integrated  To determine if PD-L1 and other potential biomarkers predict response to metformin and pembrolizumab combination	O	Pre-treatment During combination	FFPE slides	5-10 slides	[name]

## Specimen Collection Schedule

Specimen Type	Pre-treatment Day -14 (Arm 1) Day -21 (Arm 2)	Cycle 1 Day 1 (Arm 1); Day -7 (Arm 2)	Cycle 2 Day 1 (Week 4)
Peripheral Blood 60mls in 6 EDTA tubes and 5mls in 1 red top serum tube	X	X	X
FFPE slides x 20 and 1 tissue scroll	X		X

### 6.2 Integrated Correlative Studies

Please consult the study lab manual for more details.

#### NK Cell Infiltration and Tissue Biomarkers

- Collection of Specimen(s): Tumor block (if block is unavailable, 20 FFPE slides may be permissible but need verification from PI) will be collected at screening and Week 4; Archival is acceptable for pre-treatment
- Handling of Specimens(s): Normal operating procedures
- Shipping of Specimen(s): Ship per standard operating procedures; Notify CTO lab by email at [contact], ***the day of shipping the sample***.
- Site Performing Correlative Study: University of Cincinnati, [name] Laboratory

### 6.3 Exploratory/Ancillary Correlative Studies

#### Peripheral Blood Immune Phenotypes/NK Effector Functions

- Collection of Specimen(s): 6 EDTA 10ml tubes will be collected at
  - Day -21 prior to treatment that day (Arm 2), Day -14 prior to treatment that day(Arm 1), and
  - Day 1 (Arm 1) or Day -7 (Arm 2), and
  - Week 4 both arms
- Handling of Specimens(s): Do not shake or freeze tubes;
- Label each tube as follows:
- Clinical trial study number (HN1901)
- Subject's (ID) (site number, patient ID example: HN02-01)
- Date the tube was drawn (example: 2/2/2018)
- Time of blood draw (example: 15:00)
- Study time-point (example: Day 1)
  - Isolation of PBMCs to be performed after delivery to laboratory below

#### Shipping of Specimen(s):

- Place sample in absorbent pack and biohazard bag along with blood sample requisition form.

- Wrap gel pack around biohazard bag with sample and place into *ambient* shipping box.
- Follow IATA shipping instructions and standards by properly labeling all shipping boxes to prevent delays.
- Attach provided FedEx Airbill to the shipping box.
- Ship per standard operating procedures; Notify CTO lab by email at [[contact]](mailto:[contact]), ***the day of shipping the sample***.
- Samples to be shipped Monday-Thursday only via FedEx First Overnight.

Site(s) Performing Correlative Study: University of Cincinnati, [name] and [name] Laboratory

#### Cytokine Levels/ NKG2D soluble ligands

- Collection of Specimen(s): 6 EDTA 10ml tubes and 1 red top serum 5ml tube will be collected at:
  - o Day -21 prior to treatment that day (Arm 2), Day -14 prior to treatment that day(Arm 1), and
  - o Day 1 (Arm 1) or Day -7 (Arm 2), and
  - o Week 4 both arms

#### Handling of Specimens(s): Do not shake or freeze tubes;

- Label each tube as follows:
- Clinical trial study number (HN1901)
- Subject's (ID) (site number, patient ID example: HN02-01)
- Date the tube was drawn (example: 2/2/2018)
- Time of blood draw (example: 15:00)
- Study time-point (example: Day 1)
- Separation of plasma to be performed after delivery to laboratory below

#### Shipping of Specimen(s):

- Place sample in absorbent pack and biohazard bag along with blood sample requisition form.
- Wrap gel pack around biohazard bag with sample and place into ambient shipping box.
- Follow IATA shipping instructions and standards by properly labeling all shipping boxes to prevent delays.
- Attach provided FedEx Airbill to the shipping box

Ship per standard operating procedures; Notify CTO Lab by email at [[contact]](mailto:[contact]) ***the day of shipping the sample***.

Site(s) Performing Correlative Study: University of Cincinnati, CTO Laboratory and [name] Laboratory

#### STAT-3 Expression

- Collection of Specimen(s): Tumor block or 20 FFPE slides will be collected at screening and Week 4; Archival is acceptable for pre-treatment
- Handling of Specimens(s): Normal operating procedures; RNA to be extracted by

laboratory below

- Shipping of Specimen(s): Ship per standard operating procedures; Notify CTO lab by email at [[contact]](mailto:[contact]) *the day of shipping the sample*.
- Site(s) Performing Correlative Study: University of Cincinnati, [name] Laboratory

## **TREATMENT PLAN**

The Study Calendar summarizes the trial procedures to be performed at each visit. Individual trial procedures are described in detail below. It may be necessary to perform these procedures at unscheduled time points if deemed clinically necessary by the investigator.

### **7.1 Medical History**

A medical history will be obtained by the investigator or qualified designee. Medical history will include all active conditions, and any condition diagnosed within the prior 10 years that are considered to be clinically significant by the Investigator. Details regarding the disease for which the subject has enrolled in this study will be recorded separately and not listed as medical history; this will also include a history of alcohol and tobacco use. Medical history should be graded per CTCAE v.5 to aid in assessment of potential grade changes with respect to adverse events.

### **7.2 Prior and Concomitant Medications Review**

#### Prior Medications

The investigator or qualified designee will review prior medication use, including any protocol-specified washout requirement, and record prior medication taken by the subject within 28 days before starting the trial (time of consent). Treatment for the disease for which the subject has enrolled in this study will be recorded separately and not listed as a prior medication.

#### Concomitant Medications

The investigator or qualified designee will record medication, if any, taken by the subject during the trial, including all medications used in the treatment of any adverse events.

### **7.3 Disease Details and Treatments**

#### **7.3.1 Disease Details**

The investigator or qualified designee will obtain prior and current details regarding disease status.

#### **7.3.2 Prior Treatment Details**

The investigator or qualified designee will review all prior cancer treatments including systemic treatments, radiation and surgeries.

### 7.3.3 Subsequent Anti-Cancer Therapy Status

The investigator or qualified designee will review all new anti-neoplastic therapy initiated after the last dose of trial treatment. If a subject initiates a new anti-cancer therapy within 30 days after the last dose of trial treatment, the 30-day Follow-up visit must occur before the first dose of the new therapy. Once new anti-cancer therapy has been initiated the subject will move into survival follow-up.

### 7.3.4 Assignment of Screening/Study Number

All consented subjects will be given a unique screening number that will be used to identify the subject for all procedures that occur prior to eligibility being confirmed. Each subject will be assigned only one screening number. Screening numbers must not be re-used for different subjects. The University of Cincinnati will provide any sub-sites with instructions for the methods to be used in assigning screening information to potential subjects.

Any subject who is screened multiple times will retain the original screening number assigned at the initial screening visit. The screening number will be their study number as well once they are allocated to treatment.

### 7.3.5 Trial Compliance

Interruptions from the protocol specified treatment plan for greater than 4 weeks delay of pembrolizumab or metformin doses require consultation between the investigator and the University of Cincinnati PI (if not the same) and written documentation of the collaborative decision on subject management.

The total volume of pembrolizumab infused will be compared to the total volume prepared to determine compliance with each dose of pembrolizumab administered. Treatment with standard therapies will be prepared and administered as per the approved product label.

## 7.4 Agent Administration

Treatment will be administered on an outpatient basis. Reported adverse events and potential risks are described in the Investigators Brochure for Pembrolizumab and the package insert for Metformin. Appropriate dose modifications are described in Section 8. No investigational or commercial agents or therapies other than those described below may be administered with the intent to treat the patient's malignancy.

Regimen Description					
Agent	Premedications; Precautions	Dose	Route	Schedule	Cycle Length
Pembrolizumab	No premedications; No steroids	200mg or 400mg	IV over 30 minutes	Days 1, week 1 (for 400mg	21 days (3 weeks)

				dose, therapy only given q6 weeks and on odd cycles)	
Metformin*	No premedications	1000mg for first 7 days followed by 2000mg daily	Oral	Daily	Continuous**

* The patient will be requested to maintain a medication diary of each dose of medication. The medication diary will be returned to research staff at the end of each course.
 
** Metformin will be escalated per schema and then given continuously throughout pembrolizumab cycles.
					

#### 7.4.1 Metformin

##### *Treatment:*

Patients will receive metformin ER starting on day -14 for arm 1 and Day -7 for arm 2. The starting dose will be 1000mg PO daily to be administered with evening meal. The tablet should be swallowed whole, and patients will be instructed not to crush, cut or chew medication. On day -7 (or Day 1 for arm 2), patients will increase to 2000mg daily. Metformin will be continued daily with pembrolizumab.

Metformin should continue throughout treatment and even through pembrolizumab delays unless patient is experiencing adverse effects attributed to metformin. Metformin should be taken with food at approximately the same time daily. Patients will be instructed to check their blood sugar if they have any symptoms of hypoglycemia including but not limited to chills/shakiness, cold feeling, lightheadedness, dizziness, etc. Patients will be given a diary to record each dose. They should also be warned that the shell of the ER tablet may be visible in stool and not to be alarmed.

NOTE: Temporarily discontinue metformin in patients undergoing radiologic studies in which intravascular iodinated contrast media are utilized. It is generally recommended that metformin be temporarily discontinued prior to or at the time of intravascular administration of iodinated contrast media (potential for acute alteration in renal function). Continue to withhold metformin for 48 hours after the radiologic study.

## 7.5 Clinical Procedures/Assessments

### 7.5.1 Adverse Event (AE) Monitoring

The investigator or qualified designee will assess each subject to evaluate for potential new or worsening AEs as specified in the Study Calendar and more frequently if clinically indicated. Adverse events will be graded and recorded throughout the study and during the follow-up period

according to NCI CTCAE Version 5.0 and Section 11 of this protocol. Toxicities will be characterized in terms regarding seriousness, causality, toxicity grading, and action taken with regard to trial treatment.

Please refer to Section 11 for detailed information regarding the assessment and recording of AEs.

### 7.5.2 Full Physical Exam

The investigator or qualified designee will perform a full physical exam during the screening period. Clinically significant abnormal findings should be recorded as medical history. Full physical exam requires assessment of major organ sites (Constitutional, Head and Neck, Cardiovascular, Pulmonary, Abdominal, Musculoskeletal, Lymph, Neurological, and Skin).

### 7.5.3 Directed Physical Exam

Except for at screening, the investigator or qualified designee will perform a directed physical exam as clinically indicated prior to trial treatment administration.

### 7.5.4 Vital Signs

The investigator or qualified designee will take vital signs at screening, prior to the administration of each dose of trial treatment and at treatment discontinuation as specified in the Study Calendar. Vital signs should include temperature, pulse, respiratory rate, weight and blood pressure. Height will be measured at screening only.

### 7.5.5 Eastern Cooperative Oncology Group (ECOG) Performance Scale

The investigator or qualified designee will assess ECOG status (see Appendix A) at screening, prior to the administration of each dose of trial treatment and discontinuation of trial treatment as specified in the Study Calendar.

### 7.5.6 Tumor Imaging and Assessment of Disease

Pre-operative imaging will be performed at each institution and only site investigators (PI or Sub-PIs) may determine the assessment of disease recurrence.

### 7.5.7 Laboratory Safety Evaluations (Hematology, Chemistry and Urinalysis)

Laboratory tests for hematology, chemistry, urinalysis, and others are specified in Table 1.

**Table 1. Laboratory Tests**

Hematology	Chemistry	Urinalysis	Other
Hematocrit	Albumin	Blood	Serum $\beta$ -human chorionic gonadotropin†
Hemoglobin	Alkaline phosphatase	Glucose	
Platelet count	Alanine aminotransferase	Protein	Total triiodothyronine (T3) if TSH is outside

Hematology	Chemistry	Urinalysis	Other
	(ALT)		normal range
WBC (total and differential)	Aspartate aminotransferase (AST)	Specific gravity	Free thyroxine (T4) if TSH is outside normal range
Red Blood Cell Count	Lactate dehydrogenase (LDH)	Microscopic exam ( If abnormal )	Thyroid stimulating hormone (TSH)
Absolute Neutrophil Count	CO 2 or bicarbonate	Urine pregnancy test †	Prothrombin time PT/INR
Absolute Lymphocyte Count	Uric Acid		Partial Thromboplastin Time (PTT)
	Calcium		C- Peptide
	Chloride		Blood for correlative studies
	Glucose		Vitamin B-12
	Phosphorus		Lactate (Lactic acid)
	Potassium		
	Sodium		
	Creatinine		
	Magnesium		
	Total Bilirubin		
	Direct Bilirubin ( If total bilirubin is elevated above the upper limit of normal )		
	Total protein		
	Blood Urea Nitrogen		
† Done on all women of child-bearing potential. Urine or serum is acceptable.			

#### 7.5.8 Withdrawal/Discontinuation

When a subject discontinues/withdraws prior to trial completion, all applicable activities scheduled for the final trial visit should be performed at the time of discontinuation. Any adverse events, which are present at the time of discontinuation/withdrawal, should be followed in accordance with the safety requirements outlined in Section 11. Patients have the option of withdrawing from treatment only (therefore entering survival follow-up) or withdrawing from study. This should be documented clearly in REDCap.

### 7.6 Visit Requirements

Visit requirements are outlined in Section 12.0 - Study Calendar.

### 7.6.1 Screening

Potential subjects will be evaluated to determine that they fulfill the entry requirements as set forth in eligibility requirements. Visit requirements are outlined in the Study Calendar.

Results of a test performed prior to the subject signing consent as part of routine clinical management are acceptable in lieu of a screening test if performed within the specified time frame. Screening procedures are to be completed within 28 days prior to the first dose of trial treatment except for the following:

- Laboratory tests and ECOG PS are to be performed within 10 days prior to the first dose of trial treatment.
- For women of reproductive potential, a serum pregnancy test will be performed within 72 hours prior to the first dose of trial treatment. A urine test may be considered if serum test is not appropriate.

Subjects may be rescreened after initially failing to meet the inclusion/exclusion criteria and they have not yet started treatment, however, re-screening tests will not be covered by study. Results from assessments performed during the initial screening period are acceptable in lieu of a repeat screening test if performed within the specified time frame and the inclusion/exclusion criteria is met.

### 7.6.2 Treatment Period

Visit requirements are outlined in Section 12.0 – Study Calendar.

### 7.6.3 On Treatment Imaging

Patients will undergo imaging (CT of affected target areas- ideally CT with contrast unless contraindication; MRI also acceptable) every 12 weeks +/- 5 days. If patient has a PR or CR, confirmation scans are required at 4 weeks after scan in which response was first observed.

The specific method of imaging to use (CT, CT with contrast, MRI) may change per the subject's clinical needs, and this determination for which imaging method to use will rely on the treating investigator's clinical discretion.

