## **PATIENT SELECTION**

### **4.1 Eligibility Criteria**

1. Patients must have histologically or cytologically confirmed recurrent or metastatic non-cutaneous HNSCC for which there are no surgical or radiation curative options.
2. Patients may have received up to 3 prior lines of therapy for metastatic or recurrent disease.
3. Age  $\geq 18$  years.
4. ECOG performance status  $\leq 2$  (Karnofsky  $\geq 60\%$ , see Appendix A).
5. Patients must have adequate organ and marrow function as defined below:
 

– leukocytes	$\geq 3,000/\text{mcL}$
– absolute neutrophil count	$\geq 1,000/\text{mcL}$
– platelets	$\geq 75,000/\text{mcL}$
– total bilirubin	$\leq$ institutional 1.5x upper limit of normal (ULN)

- AST(SGOT)/ALT(SGPT)  $\leq 3 \times$  institutional ULN
  - creatinine  $\leq 1.5 \times$  institutional ULN
  - OR
  - glomerular filtration rate (GFR)  $\geq 50$  mL/min/1.73 m^2 (see Appendix B).
6. Human immunodeficiency virus (HIV)-infected patients on effective anti-retroviral therapy with undetectable viral load within 6 months are eligible for this trial.
  7. For patients with evidence of chronic hepatitis B virus (HBV) infection, the HBV viral load must be undetectable on suppressive therapy, if indicated.
  8. Patients with a history of hepatitis C virus (HCV) infection must have been treated and cured. For patients with HCV infection who are currently on treatment, they are eligible if they have an undetectable HCV viral load.
  9. Patients with treated brain metastases are eligible if follow-up brain imaging after central nervous system (CNS)-directed therapy shows no evidence of progression for at least 4 weeks.
  10. Patients with new or progressive brain metastases (active brain metastases) are eligible if the treating physician determines that immediate CNS specific treatment is not required and is unlikely to be required during the first cycle of therapy.
  11. Patients with a prior or concurrent malignancy whose natural history or treatment does not have the potential to interfere with the safety or efficacy assessment of the investigational regimen are eligible for this trial.
  12. Patients with known history or current symptoms of cardiac disease, or history of treatment with cardiotoxic agents, should have a clinical risk assessment of cardiac function using the New York Heart Association Functional Classification. To be eligible for this trial, patients should be class 2B or better.

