Target lesions. All measurable lesions up to a maximum of 2 lesions per organ and 5 lesions in total, representative of all involved organs, should be identified as **target lesions** and recorded and measured at baseline. Target lesions should be selected on the basis of their size (lesions with the longest diameter), be representative of all involved organs, but in addition should be those that lend themselves to reproducible repeated measurements. It may be the case that, on occasion, the largest lesion does not lend itself to reproducible measurement in which circumstance the next largest lesion which can be measured reproducibly should be selected. A sum of the diameters (longest for non-nodal lesions, short axis for nodal lesions) for all target lesions will be calculated and reported as the baseline sum diameters. If lymph nodes are to be included in the sum, then only the short axis is added into the sum. The baseline sum diameters will be used as reference to further characterize any objective tumor regression in the measurable dimension of the disease.

Non-target lesions. All other lesions (or sites of disease) including any measurable lesions over and above the 5 target lesions should be identified as **non-target lesions** and should also be recorded at baseline. Measurements of these lesions are not required, but the presence, absence, or in rare cases unequivocal progression of each should be noted throughout follow-up.

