### 13.1.3 Methods for Evaluation of Measurable Disease

All measurements should be taken and recorded in metric notation using a ruler or calipers. All baseline evaluations should be performed as closely as possible to the beginning of treatment and never more than 4 weeks before the beginning of the treatment.

The same method of assessment and the same technique should be used to characterize each identified and reported lesion at baseline and during follow-up. Imaging-based evaluation is preferred to evaluation by clinical examination unless the lesion(s) being followed cannot be imaged but are assessable by clinical exam.

Clinical lesions: Will only be considered measurable when they are superficial (*e.g.*, skin nodules and palpable lymph nodes) and  $\geq 10$  mm ( $\geq 1$  cm) diameter as assessed using calipers (*e.g.*, skin nodules). In the case of skin lesions, documentation by color photography, including a ruler to estimate the size of the lesion, is recommended.

Conventional CT and MRI: This guideline has defined measurability of lesions on CT scan based on the assumption that CT slice thickness is 5 mm (0.5 cm) or less. If CT scans have slice thickness greater than 5 mm (0.5 cm), the minimum size for a measurable lesion should be twice the slice thickness. MRI is also acceptable in certain situations (*e.g.* for body scans).

Use of MRI remains a complex issue. MRI has excellent contrast, spatial, and temporal resolution; however, there are many image acquisition variables involved in MRI, which

greatly impact image quality, lesion conspicuity, and measurement. Furthermore, the availability of MRI is variable globally. As with CT, if an MRI is performed, the technical specifications of the scanning sequences used should be optimized for the evaluation of the type and site of disease. Furthermore, as with CT, the modality used at follow-up should be the same as was used at baseline and the lesions should be measured/assessed on the same pulse sequence. It is beyond the scope of the RECIST guidelines to prescribe specific MRI pulse sequence parameters for all scanners, body parts, and diseases. Ideally, the same type of scanner should be used and the image acquisition protocol should be followed as closely as possible to prior scans. Body scans should be performed with breath-hold scanning techniques, if possible.

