#### For Patients with Measurable Disease (*i.e.*, Target Disease)

Target Lesions	Non-Target Lesions	New Lesions	Overall Response	Best Overall Response when Confirmation is Required*
CR	CR	No	CR	≥4 wks. Confirmation**
CR	Non-CR/Non-PD	No	PR	≥4 wks. Confirmation**
CR	Not evaluated	No	PR	
PR	Non-CR/Non-PD/not evaluated	No	PR	
SD	Non-CR/Non-PD/not evaluated	No	SD	Documented at least once ≥4 wks. from baseline**

PD	Any	Yes or No	PD	no prior SD, PR or CR
Any	PD***	Yes or No	PD	
Any	Any	Yes	PD	

\* See RECIST 1.1 manuscript for further details on what is evidence of a new lesion.

\*\* Only for non-randomized trials with response as primary endpoint.

\*\*\* In exceptional circumstances, unequivocal progression in non-target lesions may be accepted as disease progression.

Note: Patients with a global deterioration of health status requiring discontinuation of treatment without objective evidence of disease progression at that time should be reported as “*symptomatic deterioration.*” Every effort should be made to document the objective progression even after discontinuation of treatment.

iRECIST Note: Given that immunotherapy is being given in this protocol, patients may remain on study at first progression if investigator feels the patient is deriving clinical benefit. However, if in subsequent scans, the lesions continue to progress beyond previous scan, the patient will be considered to have progressive disease and should be taken off protocol. Any question should be discussed with the sponsor.

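### Section 7.6.3 lets the imaging method change where 13.1.3 asks for the baseline method, and its stated scan field does not secure the non-target and new-lesion assessment that the response endpoint needs

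*Combined protocol and SAP*

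**What the plan says.** **Method.** Section 7.6.3 (On Treatment Imaging) says: "The specific method of imaging to use (CT, CT with contrast, MRI) may change per the subject's clinical needs". It leaves the choice to the treating investigator. Section 13.1.3 (Methods for Evaluation of Measurable Disease) says: "The same method of assessment and the same technique should be used to characterize each identified and reported lesion at baseline and during follow-up". In its CT and MRI paragraph, 13.1.3 repeats that the follow-up modality should be the baseline one.

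**Field.** The only anatomical scope given for on-treatment scans is in 7.6.3: "CT of affected target areas- ideally CT with contrast unless contraindication; MRI also acceptable". Footnote l of the study calendar gives timing only, and section 13 sets no scan field.

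**What the assessment needs.** Section 13.1.2 requires, for non-target lesions, that their presence, absence or "unequivocal progression of each should be noted throughout follow-up". Sections 13.1.4.1 and 13.1.4.2 count any new lesion as progressive disease. In the best-overall-response table for measurable disease (13.1.4.3), the row for target PR accepts a non-target status of "Non-CR/Non-PD/not evaluated" and returns PR. A target CR with non-target lesions not evaluated also returns PR.

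**What depends on it.** Section 10.1 makes overall response the primary endpoint and PFS a secondary one. Section 10.2 calls the study successful if 6 of 19 evaluable patients respond.

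**The concern.** A site that follows 7.6.3 can depart from 13.1.3 without breaking any rule in 7.6.3. A PR needs a 30% fall in the sum of diameters and progression needs a 20% rise. If the baseline scan was contrast CT and the follow-up is non-contrast CT or MRI, part of the measured change may come from the method. That error can go in either direction.

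The field problem has one direction. If the scan covers the target areas and nothing else is imaged, progression elsewhere can go unrecorded. That can leave a patient classed as PR or SD who should be PD. It cannot do the reverse. ORR and PFS can therefore only be pushed up by it.

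**Working it through.** The plan states no figure on this point, so the check is mainly a comparison of text, followed by an illustration on an assumed rate.

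**1. Method: 7.6.3 against 13.1.3**

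| Question | 7.6.3 | 13.1.3 |
|---|---|---|
| May the method differ from baseline? | Yes, for clinical need, at the treating investigator's discretion | Same method and technique should be used |
| Which text prevails? | Not stated | Not stated |
| How is a changed-method assessment scored? | Not stated | Not stated |

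These conflict. The conflict is with the measurement methods in 13.1.3, not with the response definitions in 13.1.4.

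**2. Field: what 7.6.3 supplies against what section 13 needs**

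- Section 13.1.2 asks for target lesions representative of all involved organs, up to 2 per organ and 5 in total. Measurable disease in an involved organ will therefore usually lie within a target area.
- Only measurable lesions can be targets. Section 13.1.2 lists bone lesions, leptomeningeal disease and effusions as non-measurable, so they are always non-target. Where they lie away from the targets, the stated field does not reach them.
- A metastasis in an organ not involved at baseline is outside every baseline target area.
- Disease outside the neck is expected here: metastatic disease is eligible, and section 4.1 item 10 says "Patients with new or progressive brain metastases (active brain metastases) are eligible".
- The response table does not block a response when the non-target sites were not imaged. Nor does it say how the new-lesion column is completed for a region that was not scanned.

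The field in 7.6.3 therefore does not secure the assessment that section 13 requires. This is a gap, not an explicit contradiction.

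**3. Illustration for the 6/19 rule**

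Inputs: n = 19 and threshold 6 (section 10.2). The true ORR is set at 20%, the top of the 15-20% that section 10.2 gives for pembrolizumab alone, or at 18%, within that range. The share x of apparent responders with unseen progression is an assumption, 5% to 20%. The documents give no value.

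Formulas: observed ORR = true ORR / (1 − x); chance of success = P(X ≥ 6) for X ~ Binomial(19, observed ORR).

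| True ORR | x | Observed ORR | P(≥6 of 19) |
|---|---|---|---|
| 20% | 0 | 20.0% | 16.3% |
| 20% | 5% | 0.20/0.95 = 21.1% | 19.5% |
| 20% | 20% | 0.20/0.80 = 25.0% | 33.2% |
| 18% | 0 | 18.0% | 11.1% |
| 18% | 5% | 0.18/0.95 = 18.9% | 13.4% |
| 18% | 20% | 0.18/0.80 = 22.5% | 24.2% |

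At the low end of the assumed range the change is about 2 to 3 percentage points. At the high end the chance of meeting the rule roughly doubles.

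**4. Method error in the other direction**

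If a changed method hid an assumed 5%, 10% or 20% of true responses, then at the expected ORR of 32% the observed ORR would be 0.32 × (1 − that share) = 30.4%, 28.8% or 25.6%. P(≥6 of 19) would fall from 60.1% to 54.1%, 48.0% or 35.5%. The documents give no basis for choosing among these values either.

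**The case against.** The strongest reply is that 7.6.3 schedules scans while section 13 governs assessment, so the two can be read together. The word "only" does not appear in 7.6.3, the phrase about target areas is undefined, and no other imaging is forbidden. Section 13 still obliges the investigator to note every non-target lesion. It also gives rules for new lesions found by FDG-PET or ultrasound, so it expects findings beyond the target field. This stands to the extent that the field is an unsecured requirement and progression can be missed, not that it will be. It does not close the gap, because no text requires the wider scan and the response table does not penalise its absence.

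On method, 13.1.3 says should, allows MRI instead of CT in selected instances, and lets qualifying PET-CT be interchanged with CT. Section 7.6.3 ties a change to clinical need. That supports keeping some discretion. It does not say how a changed-method assessment counts.

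The confirmation scan at 4 weeks gives a second look, but 7.6.3 attaches no wider field and no same-method condition to it. Physical examination and the instruction to document objective progression after symptomatic deterioration may pick up some disease, but they do not replace imaging of unscanned sites.

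A reader might infer three stronger things that the documents do not support:

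- **That patients are scanned at target sites only.** The text does not say so. A brain metastasis large enough to be measurable would ordinarily be a target lesion and be scanned.
- **That sites will drop contrast to avoid interrupting metformin.** Sections 7.4.1 and 8.1 link contrast to a temporary hold, but 7.6.3 still prefers contrast CT and calendar footnote q leaves the hold to the investigator. No passage documents such a practice.
- **That the 5% to 20% range measures the bias.** It is an assumption with no source in the documents.

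**Conclusion.** The point holds at moderate severity. On method, 7.6.3 and 13.1.3 conflict and nothing resolves them, for scans that determine the primary endpoint. On field, 7.6.3 does not secure the non-target and new-lesion assessment that 13.1.2 and 13.1.4 need, and the response table lets a PR stand without it.

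Missed progression biases ORR and PFS upward. A changed method can bias ORR either way. The size cannot be derived from the documents. The probabilities shown for the 6/19 rule rest wholly on the assumed misclassification shares and on exactly 19 evaluable patients. They show that the rule is sensitive to a few misclassified patients, not that such patients will occur. The evidence does not support calling the response endpoint invalid, removing clinical discretion over imaging, or rewriting the response table.

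**What to change.** Reconcile 7.6.3 with 13.1.2 and 13.1.3, as follows:

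1. **Field.** State in 7.6.3 that on-treatment scans cover all baseline disease sites, target and non-target, over the same field as the baseline scan.
2. **Method.** State that response assessment uses the baseline modality and technique.
3. **Exceptions.** Keep the investigator's discretion where clinical need requires a different method. Document the reason and flag the time point. Count a response first seen on a changed method only if it is confirmed on like-for-like imaging.
4. **Analysis.** Leave the response table as it is. Add a sensitivity analysis of ORR for any PR scored while baseline non-target sites were not evaluated, and report the number of such patients.

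The statements on contrast and metformin in 7.4.1, 8.1 and calendar footnote q differ from one another and need their own reconciliation. This point proposes no rule for them.

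The cost is wording in one section and one extra reported analysis. Some patients would have a somewhat wider scan field, larger for those with disease at several sites, and an occasional time point would be flagged. No extra visits or patients are needed, apart from any like-for-like scan required to confirm a flagged response.
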